The treatment process concept of this ExAblate transcranial system is not different from the ExAblate body system which is currently in clinical use for some soft tissue applications (see Section 1.4). The treatment begins with a series of standard diagnostic MR images to identify the location and shape of tumor/target to be treated. The ExAblate computer uses the physician's designation of the target volume to plan the best way to cover the target volume with small spots called "sonications." These treatment spots are cylinder shaped. Their size depends on sonication power and duration. During the treatment, a specific MR scan, which can be processed to identify changes in tissue temperature, provides a thermal map of the treatment volume to confirm the therapeutic effect [71]. The thermal map is used to monitor the treatment in progress, and confirm that the ablation is proceeding according to plan, thus closing the therapy loop.

The ExAblate transcranial operates a helmet-shaped transducer (currently utilizing 1000-element phased array transducer) positioned above the subject head. The ExAblate transcranial system also includes means to immobilize the subject head, cool the interface water, and software for CT analysis and phase correction computation.

1.3.2 Rationale for ExAblate Transcranial MRgFUS Thalamotomy for the Treatment of the Essential Tremor

Both stereotactic radiofrequency (RF) lesions and deep brain stimulation (DBS) targeted to the Vim have proven effective for the treatment of ET and other tremors [27].

Ablation and stimulation have demonstrated equivalent dramatic improvements of tremors, with prospective and retrospective comparisons reporting 69-90% improvement in appendicular tremors [28, 29]. Stereotactic radiosurgery using the gamma knife (GK) is a third technique directed to the Vim thalamus to control tremor. The GK thalamotomy does not require an incision or bur hole, and has been reported to have efficacy equal to other lesion methods. Unlike the first two stereotactic techniques, the effects of the GK thalamotomy operation may require 6 months or more to develop.

Niranjan *et al.* [72] compared results of 15 gamma knife thalamotomies, 13 RF thalamotomies, and 11 thalamic DBS implants. They reported all three to be safe and effective, with each approach having advantages and disadvantages.

1.3.2.1 Risks associated with the current standard of practice in stereotactic surgery.

Hemorrhagic surgical complications

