1.3.2.2 ExAblate Transcranial MR-guided Focused Ultrasound (TcMRgFUS)

High-intensity focused ultrasound (HIFU) has been used to destroy soft tissue such as neoplasms for more than half a century [80]. Until very recently, lesioning brain by sonication has been difficult because the overlying skull absorbs most of the sound energy and distorts the transmitted acoustic waves. The landmark advance in ExAblate TcMRgFUS technology for neuro-related clinical applications occurred with the ability

of the ExAblate to sonicate through the intact cranium [42-45]. By coupling CT-based phase tuning with ExAblate, precise and small (2x2x3mm) lesions have been produced in thalamus while real-time thermal monitoring is available to observe the heating caused with each sonication [5]. Standard MR sequences have been shown to reliably predict the precise locus of tissue damage during thermal lesioning with the ExAblate system [5, 46]. The precision of the ExAblate technology has already been demonstrated in animal models [47] and in clinical trials for neuropathic pain syndromes [49], in treatment of essential tremor (IDE # G100169), and is currently being investigated in humans with brain tumors (IDE # G020182) as well as in humans with medication-refractory tremor dominant idiopathic Parkinson's disease (IDE # G120017).

1.3.2.3 Potential advantages of ExAblate TcMRgFUS Vim thalamotomy as a treatment for Essential tremor.

As a non-invasive, non-ionized MR guided procedure with real time imaging and thermal feedback, ExAblate TcMRgFUS VIM thalamotomy has several advantages for the treatment of Essential tremor:

- The treatment can be monitored in real-time with MRI and MR-thermography [56-62]. This allows for immediate confirmation of the targeting process.
- Thermal lesioning can be performed discreetly and accurately, and can be evaluated immediately.
- Unlike stereotactic radiosurgery, ExAblate TcMRgFUS does not use ionizing radiation and does not carry a risk of radiation-induced tumorigenesis.
- Because the ExAblate TcMRgFUS procedure is non-invasive, there is no scalp incision, no bur hole, and no electrode penetrating the brain. The risk of hemorrhagic complication should be reduced, and this noninvasive procedure should eliminate the risk of infectious complications.

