1.4.2 ExAblate Transcranial System

InSightec has two ExAblate Transcranial systems: mid (650 KHz) and low frequency (200 KHz). These 2 systems (medium and low range frequency) have two different characteristics:

1. Mid frequency: functional discrete lesioning for deep central locations; focal thermal lesions
2. Low frequency: tumor ablation and has wide treatment envelope

These differences are summarized in the following table:

| Table 1: Summary of main differences between the low and mid frequency ExAblate systems | |
|--|---|
| Low frequency ExAblate Transcranial System | Mid frequency ExAblate Transcranial System |
| Enables access to most of brain volume | Deep brain targets |
| Spot diameter: 4-12mm | Spot diameter: 2-6mm |
| Low frequency (~220kHz) | Medium frequency (~650kHz) |
| Support both standard and burst Sonication regimes | Support standard sonication only |
| 
Standard sonication delivers the required energy in a continuous fashion to the target
 
Burst Sonication: delivers the energy in a series of burst (high amplitude short duration of each burst of energy). The total accumulated energy is the same. The only difference is the way it is delivered to the target.
 | |

For the proposed study, the same mid-frequency ExAblate Transcranial system that was investigated for the treatment of Essential Tremor subjects (under IDE # G100169) will be used; it should be noted this same system is utilized for the FDA approved study for tremor in Parkinson's disease subjects. The system uses the same transducer, ALL clinical features and tools of this FDA ET IDE approved system version, subject interface and coupling, etc. There is no change to the thermal modeling, energy delivery, beam forming, nor treatment parameters and guidelines, and mitigating steps. Furthermore, the manufacturing process, device risk analysis, SW and HW verification and validation have also remained unchanged.

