7.2.3 Imputation of Confirmatory Secondary Endpoint 3 (SE3)

CRST Part C total score is considered missing if more than two items are missing. Missing items at 3 Months FU will be imputed using LOCF method (where applicable). The obtained (non-missing) items will be taken as is and will not be imputed.

8 Data Derivation and Transformation

Data not originally part of the CRF will be derived as follows:

- Age [years] = (Date of Informed Consent – Date of Birth + 1) / 365.25
- BMI [kg/m²] = Weight (kg) / Height (m)²
- Time from Initial ET Symptoms [years] = (Date of Informed Consent – Approximate Date of Initial ET Symptoms¹ + 1) / 365.25
- Time from Initial ET Diagnosis [years] = (Date of Informed Consent – Date of Initial ET Diagnosis¹ + 1) / 365.25
- Time from First ET Medical Therapy [years] = (Date of Informed Consent – Date of First ET Medical Therapy¹ + 1) / 365.25
- Handedness (Right / Left) is indicated by CRF field “Right or Left Handed” on Baseline CRST Form, as assessed by Site Assessor
- Treated Side of the Body (Right / Left) is defined as the opposite side of the brain being treated, indicated by CRF field “Side of Brain being treated” on the ExAblate Treatment Form
- Time Inside Scanner [min] = Time Out of Scanner – Time In Scanner
- Sonication Treatment Time [min] = Sonication End Time – Sonication Start Time
- Target Size [cm³] = $\frac{4}{3}\pi(\frac{1}{2} \times SI[cm] \times RL[cm] \times AP[cm])$, where SI, RL and AP are the target dimensions Superoinferior, Right-Left and Anteroposterior respectively, as collected on the ExAblate Treatment Form
- The following will be provided by InSightec:

¹ If only Day is missing then the 15th of the Month will be imputed; if both Day and Month are missing then the 1st of July will be imputed.

- By-subject listing of all protocol deviations
- Coding of all Adverse Events

9 Interim Analysis

No interim analysis is planned for the ET-002 study.

10 Statistical Analysis

All statistical analyses will be carried out using SAS® Version 9.2 or higher under Windows® Server 2008 Terminal.

The data will be summarized in tables listing the mean, standard deviation, minimum, median, maximum and number of subjects for continuous data, or in tables listing count and percentage for categorical data where appropriate.

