10.3 Treatment Procedure

Treatment procedure characteristics will be analyzed using the Safety analysis population.

Descriptive statistics or frequency distribution, as appropriate, by treatment group will be provided for the following:

- Pre-Treatment Characteristics (**Error! Reference source not found.**):
 - Head Condition
 - Scars or Lesions on Head
 - Was the subject "off" medication for at least 12 hours prior to the treatment?
- Vital Signs per Time Point (**Error! Reference source not found.**):
 - Systolic Blood Pressure
 - Diastolic Blood Pressure
 - Heart Rate
 - O₂ Saturation
- Treatment Characteristics (**Error! Reference source not found.**):
 - Time Inside Scanner
 - Sonication Treatment Time

- Target Size
- Minimal Energy
- Maximal Energy
- Number of Performed Sonifications
- Treated Side of the Body (Right / Left) (**Error! Reference source not found.**)
- Procedure Interruption / Early Termination:
 - Interruption:
 - Procedure interrupted for more than 30 minutes due to MR system problems (**Error! Reference source not found.**)
 - Procedure interrupted for more than 30 minutes due to ExAblate system problems (**Error! Reference source not found.**)
 - Listing of all device malfunctions (**Error! Reference source not found.**)
 - Early Termination:
 - Procedure terminated prior to completion (**Error! Reference source not found.**)
 - Listing of all termination reasons (**Error! Reference source not found.**)

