10.7 Crossover Stage Analysis

The Crossover stage includes Sham subjects who terminated the Main stage of the study with the reason “Sham subject crossed over ExAblate Arm at Month 3”. According to the protocol, these subjects undergo Active ExAblate treatment and subsequent follow-up assessments, just as defined for the ExAblate group in the Main stage of the study.

All analyses in this section will be presented based on the Crossover analysis population. Results from the Main stage under Sham treatment will be presented in parallel with results under ExAblate treatment during Crossover stage, similarly to presentation of the Main stage results.

Descriptive statistics over time by treatment group will be provided for the following:

- Confirmatory primary and secondary efficacy endpoints
- Additional secondary endpoints

In addition, where appropriate, the following will be provided:

- Graphical presentation over time by treatment group
- Statistical testing to compare:
 - between treatment groups, by visit
 - within each treatment group, comparing Baseline to each follow-up visit
 - between treated and non-treated sides, within each treatment group, by visit

11 Data Listings

[figure not shown]
Data listings will be provided for all data available.

12 Appendix

The following section presents mock tables and figures for Section 10.

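### As printed, the SAP's Target Size formula is not an ellipsoid volume: 4 times too large if SI, RL and AP are full extents, half the true value if they are semi-axes

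*SAP*

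**What the plan says.** SAP section 8 (Data Derivation and Transformation) lists variables to be computed from case report form fields. Target Size, in cm³, is one of them. Its formula is typeset as "4}{3}\pi(\frac{1}{2} \times SI[cm] \times RL[cm] \times AP[cm", that is, (4/3)π × (½ × SI × RL × AP), with one factor of one half inside a bracket that holds all three dimensions. The definition continues: "where SI, RL and AP are the target dimensions Superoinferior, Right-Left and Anteroposterior respectively, as collected on the ExAblate Treatment Form". The shape is not named, and the text does not say whether each dimension is a full extent or a semi-axis.

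SAP 10.3 places Target Size among the treatment characteristics to be described by treatment group, on this population: "Treatment procedure characteristics will be analyzed using the Safety analysis population". SAP section 10 fixes the summary statistics as "mean, standard deviation, minimum, median, maximum and number of subjects for continuous data". The other characteristics in that group are times, energies and the number of sonications, so Target Size is the only measure of target size in the table. SAP section 11 adds: "Data listings will be provided for all data available".

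**The concern.** The cm³ unit and the leading (4/3)π show that an ellipsoid volume is intended. Halving the product of three diameters once is not the same as halving each diameter: the first divides the product by 2, the second by 8. If the form records semi-axes, there should be no halving at all. All three fields are described alike, so the printed line does not match an ellipsoid under either uniform convention.

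A programmer will code a derivation rule literally. The reported mean, standard deviation, minimum, median and maximum of Target Size would then all be wrong by the same factor, in both arms. Absolute volume carries meaning for a reader of this protocol: section 1.2.1 mentions Vim volumes of about 40 mm³ as sufficient for effective treatment. On the full-extent reading, a true 10 mm³ target would be reported as about 40 mm³. The SAP plans no comparison with that figure, so this concerns how a reader may take the table and not a planned analysis.

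**Working it through.** The documents give no numerical Target Size, so there is no planned figure to reproduce. The check compares coefficients.

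**Inputs**
- Printed formula and description of SI, RL and AP: SAP section 8.
- Ellipsoid volume with semi-axes a, b, c: V = (4/3)πabc.
- Sizes for illustration only: background lesions in Protocol 1.3.2.2 ("precise and small (2x2x3mm) lesions have been produced in thalamus") and the mid-frequency system in Protocol 1.4.2, Table 1 ("Spot diameter: 2-6mm"). Neither is a target dimension from this trial.

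**Step 1. Coefficients of SI × RL × AP**
- Printed: (4/3)π × ½ = 2π/3 = 2.0944.
- Ellipsoid, full extents (a = SI/2, b = RL/2, c = AP/2): (4/3)π × ⅛ = π/6 = 0.5236.
- Ellipsoid, semi-axes: 4π/3 = 4.1888.

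**Step 2. Ratios, constant for any dimensions**
- Against full extents: 2.0944 / 0.5236 = 4.00.
- Against semi-axes: 2.0944 / 4.1888 = 0.50.

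**Step 3. Could the formula describe another shape?** On the full-extent reading the bounding box has coefficient 1, so the printed volume is 2.09 times the box that encloses the target. No shape can have that volume. Protocol 1.3.1 says of the individual spots: "These treatment spots are cylinder shaped". A full-extent cylinder has coefficient π/4 = 0.7854, and the printed formula is 2.67 times that.

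**Step 4. Is there any reading on which it is right?** Only a mixed one. If one field is a full extent and the other two are semi-axes, then (4/3)π × (SI/2) × RL × AP = 2.0944 × SI × RL × AP, which matches. Nothing in the SAP supports treating the three fields differently.

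**Step 5. Illustrations (mm³)**

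| Dimensions | SI × RL × AP | Printed formula | Ellipsoid, full extents | Ellipsoid, semi-axes |
|---|---|---|---|---|
| 2 × 2 × 3 mm | 12 | 25.1 | 6.3 | 50.3 |
| 2 mm diameter sphere | 8 | 16.8 | 4.2 | n/a |
| 6 mm diameter sphere | 216 | 452.4 | 113.1 | n/a |

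**Step 6. Where the value is used.** Target Size does not enter the primary endpoint or SE1 to SE3 (SAP 6.2.1 and 6.2.2). It is not among the covariates age, baseline CRST, gender and center (SAP 10.6.5), and it is not used in the safety analyses (SAP 10.5). SAP 10.3 plans description only. A constant multiplier leaves between-arm ratios and ranks unchanged.

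**The case against.** The strongest counter-argument concerns provenance. The finding rests on one expression converted from PDF. The bracket around the product does no work as printed. It would make sense if an exponent on the one half, or repeated halves, had been lost, or if the authors meant half of each dimension. This stands as a caution: the conclusion is about the formula as printed, and the source has to be checked. It is not shown to be a conversion loss. The expression is complete and balanced, and the superscripts in cm³ and kg/m² survived in the same section. Even if the source formula proves sound, the SAP still does not say what the three fields measure, and the formula cannot be verified without that.

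The second argument is weight. The variable is descriptive, no conclusion depends on it, and the dimensions are collected, so the volumes can be recomputed if the listings include them. That is correct and limits the finding. It does not remove the error from a table that is planned for reporting.

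Third, the direction of the error is unknown, because it depends on a form that is not in the documents. This also stands: the factor of 4 should not be quoted without the alternative of one half. The illustrative sizes describe background lesions and single spots, and they add nothing to the ratios beyond scale.

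**Conclusion.** The concern holds as stated. With all three fields on the same convention, the printed formula gives 4.0 times the ellipsoid volume if they are full extents and 0.5 times if they are semi-axes. The wording of the SAP reads most naturally as full extents, in which case the result is impossible for any shape, at 2.09 times the bounding box. Which factor applies is not settled by the documents.

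This rests on two assumptions: that the formula in the source is as it appears in the converted text, and that the three fields share one convention. The arithmetic is exact, and the remaining uncertainty lies in those two points. The damage is confined to the absolute Target Size values in the SAP 10.3 table. Efficacy and safety conclusions are untouched.

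**What to change.** 1. Compare the formula with the source PDF and with the derivation program.
2. Confirm from the ExAblate Treatment Form whether SI, RL and AP are full extents or semi-axes, and that they are in cm. State this in SAP section 8.
3. If they are full extents, use Target Size [cm³] = (4/3) × π × (SI/2) × (RL/2) × (AP/2) = (π/6) × SI × RL × AP. If they are semi-axes, use (4/3) × π × SI × RL × AP.
4. Correct the program behind the SAP 10.3 table to match, and include the three dimensions in the section 11 listings.
5. Add a check that no full-extent Target Size exceeds SI × RL × AP. The corrected formula always passes, since π/6 is below 1, so the check only catches the old line left in the code.

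The cost is one look at the form, one line of SAP text and one line of code.

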10.1 Subject Disposition

The following will be provided based on all recruited subjects:

- Subject disposition flow chart (Figure 1)
- Frequency distribution of answers (Yes / No) to inclusion / exclusion criteria
(Error! Reference source not found., Error! Reference source not found.)
- Frequency distribution of overall eligibility for the study (Yes / No) based on inclusion / exclusion answers **(Error! Reference source not found.)**
- Listing of screen failures along with the reason for not entering the study
(Error! Reference source not found.)
- Subject accountability by visit and treatment group **(Error! Reference source not found.)**
- By-subject listing of all protocol deviations **(Error! Reference source not found.)**

The following will be provided using Safety analysis population:

- Number and percentage of subjects in each of the analysis populations by treatment group (**Error! Reference source not found.**)
- Listing of subjects excluded from each of the analysis populations along with the reason for exclusion (**Error! Reference source not found.**)

The following will be provided using ITT analysis population:

- Number and percentage of subjects by center and treatment group (**Error! Reference source not found.**)
- Termination of the Study Main Stage:
 - Number and percentage of subjects who completed / prematurely discontinued the first 3 months FU of the study Main stage by treatment group (**Error! Reference source not found.**)
 - Number and percentage of subjects who completed / prematurely discontinued the follow up period (from 3 up to 12 months) of the study Main stage for ExAblate group only (**Error! Reference source not found.**)
 - Listing of all dropouts along with reason for termination, treatment group and last available visit (**Error! Reference source not found.**)

The following will be provided using Crossover analysis population:

- Number and percentage of subjects by center (**Error! Reference source not found.**)
- Termination of the Study Crossover Stage:
 - Number and percentage of subjects who completed / prematurely discontinued the study crossover stage (**Error! Reference source not found.**)
 - Listing of all dropouts along with reason for termination and last available visit (**Error! Reference source not found.**)
- Subject accountability by visit (**Error! Reference source not found.**)

10.2 Baseline Characteristics

Baseline characteristics will be analyzed using the Safety analysis population.

Descriptive statistics or frequency distribution, as appropriate, by treatment group will be provided for the following:

- Demographic Characteristics and Vital Signs:
 - Age, BMI, Height, Weight (**Error! Reference source not found.**)
 - Gender, Race (**Error! Reference source not found.**)
- Medical History:
 - Significant medical conditions (other than the present disease) (**Error! Reference source not found.**)
 - Other significant medical conditions (protocol specific) (**Error! Reference source not found.**)
- Essential Tremors History:
 - Time from Initial ET Symptoms (**Error! Reference source not found.**)
 - Time from Initial ET Diagnosis (**Error! Reference source not found.**)
 - Time from First ET Medical Therapy (**Error! Reference source not found.**)
 - Family History of ET (**Error! Reference source not found.**)
 - Listing of subjects having family history of ET along with specification of relationship degree and the number of relatives (**Error! Reference source not found.**)
 - Indication of etiology due to neuroleptic drug exposure (**Error! Reference source not found.**)
 - Is subject considered medication refractory? (**Error! Reference source not found.**)
- MRI Examination (**Error! Reference source not found.**):
 - Any arteriovenous malformations that require treatment
 - Any aneurysms that require treatment
 - Evidence of a recent hemorrhage
- CT Examination (**Error! Reference source not found.**):
 - Any calcifications present within the treated area
 - Any implants within the skull or brain
 - Is the skull suitable for treatment?
 - History of DVT or systemic thrombosis

- Evidence of acute thrombosis in lower extremities for subjects who had a history of DVT or systemic thrombosis
- CRST and QUEST questionnaire parameters at Baseline, as defined in Sections 6.2.1 and 6.2.2 (**Error! Reference source not found.**):
 - The Treated (Contralateral) Upper Extremity CRST Sub Score (CRST_[contralateral, Baseline])
 - QUEST Summary of Dimensions Total Score (QUEST_[Baseline])
 - Functional Disabilities CRST Part C Total Score (CRST_C_[Baseline])

Where applicable, baseline characteristics will be compared between treatment groups using two-sided t-test for continuous normal variables, Wilcoxon rank-sum test for continuous variables with distribution deviating from normal and Fisher's Exact test for categorical variables (**Error! Reference source not found.**).

